11.1.3. Third Interim Analysis

A third interim analysis is planned, preferably at the end of a hemispheric RSV season, when approximately 70 to 80 subjects from Cohort 2 have completed the Day 14 assessments (or discontinued earlier) and will include all available data from Cohort 1 and Cohort 2. Enrollment in the >3 days to ≤5 days since symptom onset stratum might be temporarily paused prior to interim analysis 3 (at N approximately 70-80 in Cohort 2), once the maximum number of subjects are enrolled in the >3 days to ≤5 days since symptom onset stratum in Cohort 2. Enrollment in the >3 days to ≤5 days since symptom onset stratum will be reopened once the last subject required for interim analysis 3 has been randomized. During this interim analysis, a futility and population enrichment analysis will be performed on antiviral activity (data from both cohorts combined) and clinical endpoints (Cohort 2 data only). The rules implement simultaneously a conditional success probability approach (viral load) and a Go-NoGo approach¹⁰ on multiple clinical endpoints. Both the study team and the IDMC will review the results of the interim analysis, and may recommend to the Sponsor Committee an early termination of the study for futility or to enrich the population and limit further enrollment to patients with ≤3 days since symptom onset, in case the conditional power on the viral load endpoint is regarded as being too low and/or the success probability of the clinical endpoints is too low. The Sponsor Committee will take a decision considering the recommendation of the study team and the IDMC (see also Section 11.12). The exact criteria of these non-binding decision rules will be defined in the SAP.

No clinical endpoints for Phase 3 have been identified yet and the association between the antiviral effect and clinical course endpoints is not yet established for RSV. A key secondary objective of this Phase 2 study is the evaluation of clinical course endpoints and their dependence on viral load reductions. Results of this Phase 2 study will inform on discussion and selection of clinical course endpoints and guide the design for subsequent Phase 3 studies. Therefore, a sample size re-estimation based on clinical course endpoints (Cohort 2 data only) will be performed during interim analysis 3 and may result in an expansion of Cohort 2. Based on all available data from Cohort 2 at the cut-off for interim analysis 3, one or more clinically relevant and sensitive endpoint(s) will be selected for confirmation. Time to resolution (ie, to none or mild symptoms) and reduction in severity of selected clinical signs/symptoms of RSV-related illness are currently

expected to be the most relevant clinical endpoints for Phase 3 planning. However, data from this study, in combination with data from other RSV studies within and outside the company, and knowledge obtained through health authority interaction(s) will be considered in interim analysis 3 for the endpoint selection and sample size recalculation.

After selection of (a) clinical endpoint(s), the number of subjects in Cohort 2 will be calculated to minimize the conditional “consider”-probability for clinical endpoints (Go-NoGo-approach) at the end of the study assuming a required confidence of 90% (one-sided) to exclude the target value and/or the minimal acceptable value.

Both the study team and the IDMC may recommend to the Sponsor Committee an increase of the sample size for Cohort 2 of the study. The maximum number of subjects in Cohort 2 in the study will not exceed 300.

11.1.4. Fourth Interim Analysis

If the study is extended beyond the initially planned sample size in Cohort 2 for the primary analysis (N 150), a fourth interim analysis will be performed preferably at the end of a hemispheric RSV season, after approximately 150 subjects in Cohort 2 have completed the Day 14 assessments (or discontinued earlier), and will include all available data from Cohort 1 and Cohort 2. Enrollment in the >3 days to \leq 5 days since symptom onset stratum might be temporarily paused prior to interim analysis 4 (at N approximately 150 in Cohort 2), once the maximum number of subjects are enrolled in the >3 days to \leq 5 days since symptom onset stratum in Cohort 2. Enrollment in the >3 days to \leq 5 days since symptom onset stratum will be reopened once the last subject required for interim analysis 4 has been randomized. The primary analysis on antiviral activity will be performed during this fourth interim analysis and effects of JNJ-53718678 on clinical course endpoints, next to endpoints related to safety, PK and PK/PD, will be analyzed to support early Phase 3 preparations, including regulatory interactions. In addition, the futility and population enrichment analysis will be repeated at this interim analysis. Both the study team and the IDMC will provide their recommendations to the Sponsor Committee, who will decide, taking all recommendations into account.

The final analysis is planned when all subjects from Cohort 1 and Cohort 2 have completed the study (or discontinued earlier). If no extension of Cohort 2 is required, the final analysis will coincide with the primary analysis. Enrollment in the >3 days to \leq 5 days since symptom onset stratum will be stopped once the maximum number of subjects are enrolled in this stratum in both cohorts. Since the number of subjects enrolled in Cohort 2 is the trigger to perform interim analysis 3 and interim analysis 4, enrollment in Cohort 1 in the >3 days to \leq 5 days since symptom onset stratum might be stopped, at any time after interim analysis 2, once the maximum number of subjects in this stratum are enrolled for the final analysis.

While recruitment in the subcohort of Cohort 1 is ongoing, subjects >2 and \leq 3 years of age are not allowed to be enrolled in Cohort 2, even if enrollment in that cohort has been opened for the age groups \leq 2. After 6 subjects of the subcohort are evaluable for PK analysis and have completed the Day 14 assessments (or discontinued earlier), safety and PK data will be reviewed by the IDMC,

who will issue its recommendation to the sponsor, based on which the Sponsor Committee will decide whether to also initiate enrollment of subjects >2 and ≤ 3 years of age in Cohort 2 when enrollment in that cohort has been opened for the age groups ≤ 2 . During this IDMC review, additional subjects >2 and ≤ 3 years of age can be enrolled in Cohort 1 and will follow all Cohort 1 procedures.

To account for multiplicity, and to be able to define a robust clinical course endpoint for Phase 3, both unadjusted and adjusted p-values, with appropriate Type I error control, will be presented in the final analysis.

11.2. Subject Information

For all subjects who received at least 1 dose of study drug, descriptive statistics will be provided.

All demographic (eg, age, length, weight, race, gender) and other initial subject characteristics (physical examination [length, body weight, head circumference], medical and surgical history, family history, concomitant diseases, RSV disease characteristics) will be tabulated and analyzed descriptively by treatment group.

11.3. Sample Size Determination

11.3.1. Primary Objective: Establish Antiviral Activity

The basis of the sample size calculation is the antiviral results of Study 53718678RSV1005. In that study, the mean difference in RSV viral load AUC from baseline until Day 5 of the placebo group versus active (adjusted for baseline viral load) was estimated as $105 \log_{10}$ copies.hour/mL (corresponding to a 25% reduction) and the standard deviation (SD) on the RSV viral load AUC as $85 \log_{10}$ copies.hour/mL (corresponding to a CV of approximately 20%).

Assuming a more conservative reduction in RSV viral load AUC of 20% compared to placebo, considering a CV of 35% (slightly higher variability than observed in Study 53718678RSV1005), and a 1-sided alpha of 2.5%; the power to conclude a dose-response using the Multiple Comparison Procedure-Modeling (MCP-Mod) procedure under different assumptions for the dose-response relationship (linear, E_{max} , and exponential,) is provided in [Table 5](#). Based on Study 53718678RSV1005 results, no discrimination between the proposed doses is expected (ie, E_{max} dose-response shape was observed).

Table 5: Power (%) to Conclude Dose-response Using MCP-Mod Under Different Assumptions for the Dose-response Relationship

Assumed CV	Assumed dose-response relationship		
	Linear	E_{max}	Exponential
	Cohort 1 + Cohort 2 (N=74 per treatment arm)		
20%	100.0	100.0	100.0
35%	92.3	95.3	96.6
Cohort 2 only (N=50 per treatment arm)			
20%	99.8	100.0	100.0
35%	79.0	84.0	86.9
Cohort 1 only (N=24 per treatment arm)			
20%	91.5	94.7	96.2
35%	47.1	51.2	54.7

If data of both cohorts are combined (N 74 per treatment arm), the power to conclude dose-response is more than 90% for all 3 different assumptions for the dose-response relationship. If data from Cohort 1 cannot be combined with data from Cohort 2 (eg, due to inconsistency [means and/or variability] in viral load data between cohorts per treatment group), the power to conclude a dose-response using the MCP-Mod procedure in Cohort 2 (N 50 per treatment arm) is at least 79%.

The sample size in Cohort 1 only (N \geq 24 per treatment arm) will provide sufficient power (approximately 90%) if the reduction in RSV viral load AUC is at least 20% with a CV which is not higher than observed in Study 53718678RSV1005 (ie, 20%).

In conclusion, a sample size of 72 in Cohort 1 and 150 in Cohort 2 is sufficient to detect with reasonable power the antiviral effect; even if the data of Cohort 1 cannot be combined with the data of Cohort 2. Therefore, the primary analysis will be performed after approximately 150 subjects from Cohort 2 have completed the Day 14 assessments (or discontinued earlier). By that time, it is expected that at least 72 subjects from Cohort 1 will have completed the Day 14 assessments (or discontinued earlier).

11.3.2. Key Secondary Objective: Clinical Course Effect

During interim analysis 3 (when approximately 70 to 80 subjects from Cohort 2 have completed the Day 14 assessments [or discontinued earlier]; see Section 11.1.3), a sample size re-estimation will be performed to allow an extension of Cohort 2 for the confirmation of the results on selected clinical course endpoints. Based on all clinical course data from Cohort 2 available at the time of the cut-off for the third interim analysis, one or more clinically relevant and sensitive endpoint(s) will be selected for confirmation in the final analysis. Time to resolution (ie, to none or mild symptoms) and reduction in severity of selected clinical signs/symptoms of RSV-related illness are currently expected to be the most relevant clinical endpoints for Phase 3 planning. However, data from this study, in combination with data from other RSV studies within and outside the company, and knowledge obtained through health authority interaction(s) will be considered in interim analysis 3 for the endpoint selection and sample size recalculation for Cohort 2.

After selection of (a) clinical endpoint(s), the number of subjects in Cohort 2 will be calculated that is required to minimize the conditional “consider”-probability for clinical endpoints (Go-NoGo-approach) at the end of the study, assuming a required confidence of 90% (1-sided) to exclude the target value and/or the minimal acceptable value.

For Cohort 1, assuming a median time to resolution of symptoms of 3 days in the placebo group, a 1-day reduction in the active group (ie, ratio of 66%), and a scale parameter of 1/0.65, a sample size of 48 subjects per treatment arm will reach 95% probability to reach an observed effect in the right direction; based on estimates derived from an accelerated failure time model. This will allow the evaluation of clinical course endpoints in the hospital population compared to the outpatients.

11.4. Efficacy Analyses

[figure not shown]
The primary population for the efficacy/antiviral activity analysis will be the intent-to-treat infected population consisting of all randomized subjects who received at least one dose of study treatment and who have a centrally confirmed RSV viral load of $\geq 1 \log_{10}$ copies/mL above the LLOQ at baseline.

11.4.1. Antiviral Effect

11.4.1.1. Primary Endpoint

The primary objective is to establish antiviral activity of JNJ-53718678. The primary efficacy endpoint is the RSV viral load area under the curve (AUC) from immediately prior to first dose of study drug through Day 5 derived from the RSV viral load as measured by a qRT-PCR assay in nasal swabs. A hybrid methodology that combines aspects of multiple testing with modeling techniques (MCP-Mod) will be used for evaluating dose-response trends and estimating the dose-response relationships. Refer to Section 2.1.

A set of 3 candidate models will be used to cover a suitable range of possible dose-response shapes (linear, E_{max} , exponential) (see [Figure 3](#)). Doses of the different age groups will be pooled and transformed to the total daily dose of the oldest age group: low dose (3 mg/kg), high dose (9 mg/kg), and placebo (0 mg/kg) and these will be used for the “treatment groups” in the analysis.

Figure 3: Candidate Models for RSV Viral Load AUC From Baseline Until Day 5

AUC values with corresponding covariance matrix will be determined by modeling the \log_{10} viral load values over time using a restricted maximum likelihood-based repeated measures approach. Analyses will include the fixed, categorical effects of treatment, strata, visit, and treatment-by-visit interaction, as well as the continuous, fixed covariates of baseline \log_{10} viral load and baseline \log_{10} viral load by-visit interaction. An unstructured (co)variance structure will be used to model the within subject errors over time. The Kenward-Roger method will be used to approximate the degrees of freedom.

Each of the dose-response shapes in the candidate set will be tested using the corresponding contrast *t*-test statistic, employing a critical value derived for the maximum of the *t*-test statistics (based on the associated multivariate *t*-distribution) to ensure appropriate multiplicity correction that preserves the Type I error rate. A dose-response trend is established when the maximum of the *t*-test statistics exceeds the critical value.

Details will be provided in the SAP that will be finalized before the first formal interim analysis.

11.4.1.2. Secondary Endpoints

The other antiviral endpoints will be analyzed graphically and descriptively as described in the SAP. For continuous variables, descriptive statistics (n, mean, SD, median, minimum, and maximum) will be calculated. For categorical variables, frequency tables will be presented. Kaplan-Meier Curves will be produced to graphically describe the time to event data.

Differences between treatment groups in viral load will be derived from the same model as for the primary endpoint using appropriate contrasts deriving least square mean differences, including the 95% 2-sided CIs. Other covariates as well as interaction effects might also be investigated.

The time to undetectable RSV viral load will be analyzed using Kaplan-Meier plots and will be modeled using an accelerated failure time model, adjusted for covariates, such as strata and baseline viral load, to estimate differences between treatment groups. A generalized MCP-Mod approach will be used to test for existence of dose-response, if applicable. For the MCP-Mod approach, doses of the different age groups will be pooled and transformed to the total daily dose of the oldest age group: low dose (3 mg/kg), high dose (9 mg/kg), and placebo (0 mg/kg) and these will be used for the "treatment groups" in the analysis.

More details regarding the analysis of these data will be described in the SAP.

11.4.2. Clinical Course of RSV Infection

All endpoints will be analyzed graphically and descriptively as described in the SAP. For continuous variables, descriptive statistics (n, mean, SD, median, minimum, and maximum) will be calculated. For categorical variables, frequency tables will be presented.

Time to-variables (eg, time to resolution of symptoms, time to clinical stability, length of hospital stay) will be analyzed using Kaplan-Meier plots and will be modeled using an accelerated failure time model, adjusted for covariates, such as strata and baseline viral load, to estimate differences between treatment groups. 80% and 95% 2-sided CIs will be calculated. A generalized MCP-Mod approach defined as in Section 11.4.1.1 will be used to test for existence of dose-response.

Parent(s)/caregiver(s) PRESORS and clinician PRESORS scores will be descriptively summarized by treatment group and compared between treatment groups. 80% and 95% 2-sided CIs will be calculated. A generalized MCP-Mod approach as defined in Section 11.4.1.1 will be used to test for existence of dose-response on parent(s)/caregiver(s) PRESORS and clinician PRESORS scores. For the MCP-Mod approach, doses of the different age groups will be pooled and transformed to the total daily dose of the oldest age group: low dose (3 mg/kg), high dose (9 mg/kg), and placebo (0 mg/kg) and these will be used for the "treatment groups" in the analysis.

Clinical course endpoints will be evaluated in Cohort 1 and Cohort 2 separately and will be compared between the 2 cohorts.

More details regarding the analysis of these data will be described in the SAP.

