Study participants will be identified when they are hospitalized or expected to be hospitalized within 24 hours after presentation to the hospital (Cohort 1) or present for medical care as outpatients (Cohort 2) with symptoms of an acute respiratory illness supporting a diagnosis of RSV infection (eg, nasal congestion, rhinorrhea, pharyngitis, increased respiratory effort, abnormal breathing sounds [wheezing, rales, or rhonchi], cyanosis, cough, apnea, fever, feeding difficulties, dehydration). For newly enrolled subjects in Cohort 2 after Protocol Amendment 6, cough or wheezing should be accompanied by at least one additional LRTI sign/symptom in order to be eligible. In Cohort 1, a subcohort of 6 subjects >2 and ≤ 3 years will be included, who will follow in general the same assessment schedule as for all subjects enrolled in Cohort 1, although with a specific PK sampling schedule, assigned at randomization (see [Section 9.4.1](#)). Of note, if the subcohort is fully enrolled, additional subjects >2 and ≤ 3 years of age can be enrolled in Cohort 1 and will follow all Cohort 1 procedures.

Overall, for both cohorts, the study will include a Screening Period (Day -1 to Day 1), a Treatment Period (Day 1 to Day 8), and a Follow-up Period (Day 9 to Day 28 [± 3]). The total study duration for each subject will be approximately 29 days (Screening included). A diagram of the study design is provided in [Figure 1](#).

Figure 1: Schematic Overview of the Design of Study 53718678RSV2002

^a In case of ongoing adverse event(s)

Note: Age group 1: ≥28 days and <3 months of age; Age group 2: ≥3 months and <6 months; Age group 3: ≥6 months and ≤3 years

Note: Prior to Protocol Amendment 4, the total daily dose was the same but the daily dosing frequency was qd instead of bid.

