Clinical outcome assessments as performed separately by the clinician (clinician PRESORS) and the parent(s)/caregiver(s) (parent[s]/caregiver[s] PRESORS, temperature log) will be captured in an electronic device. Symptoms reported in these assessments will not be reported as AEs but constitute a part of the efficacy evaluations.

An electronic device will be provided to the subject's parent(s)/caregiver(s) at the time of screening, after enrollment of the subject. The investigator/study site personnel will provide sufficient information to enable the subject's parent(s)/caregiver(s) to complete these assessments. The parent(s)/caregiver(s) PRESORS assessment should be completed once at screening, then bid (in the morning and in the evening) from Day 1 (day of first dose) to Day 14 and then once daily in the evening until the Day 21 visit. The final parent(s)/caregiver(s) PRESORS assessment has to be completed during the scheduled Day-21 on-site visit (see also [TIME AND EVENTS SCHEDULE](#)). The first parent(s)/caregiver(s) PRESORS of the bid schedule on Day 1 needs to be completed as close as feasible and prior to the first administration of study drug. The screening parent(s)/caregiver(s) PRESORS assessment will be accepted as baseline if completed within 4 hours before randomization.

During hospitalization (Cohort 1), body temperature will be measured by the investigator. On the day of discharge (Cohort 1) or at screening (Cohort 2), the initial measurement of body temperature should be performed by the investigator. If discharged (Cohort 1) or screened in the morning, only the evening assessment of the bid schedule for the measurement of body temperature should be recorded in the temperature log on the electronic device ([Attachment 8](#)).

The parent(s)/caregiver(s) PRESORS and temperature log should preferably be completed by the same person throughout the study. A second parent/caregiver who frequently provides direct care of the child can be set up as a backup reporter on the electronic device to ensure assessments are recorded if the primary parent/caregiver is unable to enter information for any reason.

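### Section 11.4.2 names strata and baseline viral load as example covariates for time to symptom resolution but not baseline symptom severity; adding it is a near-free, minor improvement

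*Protocol*

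**What the plan says.** Protocol section 11.4.2 treats the two kinds of clinical endpoint differently.

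- **Time-to-event endpoints**, including time to resolution of symptoms: Kaplan-Meier plots and an accelerated failure time (AFT) model "adjusted for covariates, such as strata and baseline viral load, to estimate differences between treatment groups". Section 11.4.1.2 has the same clause for time to undetectable RSV viral load.
- **PRESORS scores**: "PRESORS and clinician PRESORS scores will be descriptively summarized by treatment group and compared between treatment groups". No covariate is named. Dose-response is handled by reference: "A generalized MCP-Mod approach as defined in Section 11.4.1.1 will be used to test for existence of dose-response on parent(s)/caregiver(s) PRESORS". In section 11.4.1.1 the repeated-measures model is for log10 viral load: "Analyses will include the fixed, categorical effects of treatment, strata, visit, and treatment-by-visit interaction", plus baseline log10 viral load and its interaction with visit.

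Section 11.4.2 closes with "More details regarding the analysis of these data will be described in the SAP".

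Baseline severity is available. Caregiver PRESORS is completed before the first dose on Day 1, and section 9.2.2 adds: "The screening parent(s)/caregiver(s) PRESORS assessment will be accepted as baseline if completed within 4 hours before randomization". The Time and Events Schedule has clinician PRESORS at screening. Section 2.1.2 defines resolution as symptoms down to none or mild. Section 2.1.1 lists baseline disease severity among the characteristics whose effect on clinical course is a secondary objective. Section 5 stratifies on time since symptom onset and risk factors for severe disease, not on current severity.

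**The concern.** The primary model follows a sound rule: adjust an outcome for its own baseline. The adjustment clause for time to resolution keeps the virology wording, so the baseline covariate it names belongs to another outcome. A child who starts with severe symptoms has further to go to reach none or mild than one who starts just above that line. The stratification factors do not measure that distance.

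The endpoint carries weight. Time to resolution is the clinical endpoint in the futility and enrichment analysis at interim analysis 2 (section 11.1.2). Cohort 2 clinical endpoints enter the futility and enrichment rules and the sample-size re-estimation at interim analysis 3 (section 11.1.3). That analysis has 70 to 80 Cohort 2 children in three arms, about 25 per arm. With groups that small, chance imbalance in starting severity can move an unadjusted estimate, and intervals are wider than they need to be if severity is prognostic.

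**Working it through.** **Inputs.** Section 11.3.2 gives the only stated design figure for a clinical endpoint, for Cohort 1: "assuming a median time to resolution of symptoms of 3 days in the placebo group", a 1-day reduction (ratio 66%), scale parameter 1/0.65 = 1.538, 48 per arm, and 95% probability that the observed effect is in the right direction. Allocation is 1:1:1.

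**Step 1: reproduce the 95%.** With no censoring, P(right direction) = Φ(−ln(ratio)/SE), where SE = scale × √(1/n₁ + 1/n₂).

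- Pooled active (96) vs placebo (48): SE = 1.538 × √(1/96 + 1/48) = 0.272. For ratio 2/3, 0.405/0.272 = 1.49, giving 93.2%; ratio 0.66 gives 93.7%.
- One active arm vs placebo (48 vs 48): SE = 1.538 × √(2/48) = 0.314. This gives 90.2% (ratio 2/3) or 90.7% (0.66).
- Log-logistic model with scale 0.65, 48 vs 48, SE multiplied by √3: 96.1% to 96.5%.
- Weibull simulation, scale 1/0.65, censored at Day 21 (1,500 runs): 92.7% pooled, 89.2% one arm.

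The protocol does not say which contrast or distribution was used. Two readings come within 2 points of 95%, so the figure is not disputed here.

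**Step 2: effect of the extra covariate.** Let ρ be the partial correlation of baseline severity with log time after strata and viral load. Treating log time as linear in the covariates, the variance of the treatment contrast is multiplied by 1 − ρ², interval width by √(1 − ρ²), and effective sample size by 1/(1 − ρ²). The documents give no ρ, so a range is assumed. The probabilities use ratio 2/3 and scale 1/0.65.

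| ρ (assumed) | Variance cut | Interval width factor | 48 per arm acts like | Right direction, pooled | Right direction, one arm |
|---|---|---|---|---|---|
| 0 | 0% | 1.00 | 48 | 93.2% | 90.2% |
| 0.2 | 4% | 0.98 | 50 | 93.6% | 90.6% |
| 0.3 | 9% | 0.95 | 53 | 94.1% | 91.2% |
| 0.4 | 16% | 0.92 | 57 | 94.8% | 92.1% |
| 0.5 | 25% | 0.87 | 64 | 95.7% | 93.2% |

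**Step 3: at interim analysis 3.** With 25 per arm and the same scale (a Cohort 1 input borrowed for Cohort 2), the half-width of the two-sided 80% interval on the log ratio is 1.2816 × 1.538 × √(2/25) = 0.558. It becomes 0.532 at ρ = 0.3 and 0.483 at ρ = 0.5.

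**The case against.** The strongest reply is that this is a silence, not an error. The covariates are introduced by way of example, nothing excludes severity, and section 11.4.2 sends the detail to the SAP, where such lists normally sit. That stands, and it limits the point to a suggestion. What remains is that the protocol does choose examples for time to resolution, and they are the ones written for a virological outcome.

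Four stronger readings are tempting, and the protocol does not support them.

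- *PRESORS scores will be analysed with viral load as their baseline covariate.* The cross-reference is to the MCP-Mod approach. In section 11.4.1.1 the repeated-measures model is described as the way viral-load AUC values are obtained. Carried over by analogy, it would bring in baseline PRESORS. Change from baseline in PRESORS is also an endpoint in its own right, which uses the baseline in part.
- *The Go-NoGo decision gains a known amount of power.* With 48 per arm, ratio 0.66 and scale 1/0.65, the chance that a one-sided 90% bound excludes no effect rises from 52% to 60% at ρ = 0.5. But the rule in section 11.1.3 concerns a target and a minimal acceptable value in Cohort 2, which the protocol does not quantify, while these inputs are for Cohort 1.
- *Amendment 6 widened the spread of baseline severity.* Section 3.1 says "For newly enrolled subjects in Cohort 2 after Protocol Amendment 6, cough or wheezing should be accompanied by at least one additional LRTI sign/symptom". That raises the entry floor; whether the spread grows or shrinks depends on the enrolment mix, which is not given.
- *Viral load should be replaced.* Nothing argues for removing it.

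The protocol's Introduction also reports viral load and symptom severity as closely correlated in all but one of the studies it cites. Viral load may therefore already capture some of the gain, and ρ must be read as a partial correlation.

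**Conclusion.** The point holds as a minor improvement. Section 11.4.2 does not name baseline symptom severity for time to resolution, and names no covariate at all for PRESORS scores, although the measure is collected before dosing and the event is defined on the same symptoms. If the partial correlation is between 0.3 and 0.5, the variance falls by 9% to 25%. On the protocol's own measure the probability moves by about 1 to 2.5 points (93.2% to 94.1% or 95.7%, pooled), where there is little room to rise. At ρ = 0.2 the gain is slight.

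These sizes rest on an assumed ρ, no censoring, a linear model for log time and Cohort 1 inputs. A reader might infer that the trial does give up this precision. That is not established: the SAP may already include the covariate. No stated figure is wrong, and no passages contradict each other here.

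**What to change.** In section 11.4.2, add the baseline PRESORS severity of the endpoint analysed to strata and baseline viral load: the caregiver baseline for caregiver scores and time to resolution, the clinician baseline for clinician scores. State that the same model is used at the interim and final analyses. First check whether the SAP already does this; if so, only the protocol wording needs aligning.

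Do not carry over a baseline-by-visit interaction at every diary entry. Caregiver PRESORS is twice daily for 14 days and then once daily to Day 21, or 14 × 2 + 7 = 35 assessments, too many interaction terms for about 25 children per arm. Omit the interaction, or limit it to a few summary visits.

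The cost is one sentence and about one degree of freedom per model, with no added procedure or child.
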